Appendix 1: Example of CMR task sheet for treatment partner

Task number:	1
Task name:	Spatial discrimination and comparison between affected and unaffected arms.
Task description	In this exercise the therapist positions the patient's unaffected hand in a grid position and asks the patient to position her affected hand in the same positioning the opposite grid to 'mirror' the unaffected hand.
Material required	A table, and table grid (optional)
Patient position	Comfortable sitting position in a chair both arms resting in a table.
Modality	Patient with eyes closed. Therapist to move patients' unaffected arm into a position. Patient prompted to match (i.e. to mirror) the position with affected arm paying attention to the position on the arm rather than pain. Encouraged patient to verify by opening eyes.
Number of repetitions	____ repetitions
Photos	 

Appendix 2: Example of rehabilitation diary for the home-based intervention

Please insert date and total duration of the session:				
Task number:				
Able to complete?	Yes	No, provide the reason:		
Total time task (in minutes) and number of repetitions	___ min.	___ repetitions		
Patient was able to answer correctly	Yes, always	Yes, often	Yes, sometimes	Not at all
Any adverse effects (including symptom flare)	Yes, please describe	No		
Task number:				
Able to complete?	Yes	No, provide the reason:		
Total time task (in minutes) and number of repetitions	___ min.	___ repetitions		
Patient was able to answer correctly	Yes, always	Yes, often	Yes, sometimes	Not at all
Any adverse effects (including symptom flare)	Yes, please describe	No		

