Intervention phase:

The CMR home-intervention involves the recommended treatment plan being delivered by the treatment partner over a four-week period. The CRPS patient and treatment partner can refer to the written guidance provided for the different recommended tasks (an example can be found in the Appendix section 1). As part of a feasibility study the CRPS-patient and treatment partner would have agreed with [name] about the duration and frequency of the intervention sessions and this will be recorded in the written treatment plan. [name] will encourage treatment partner to deliver the intervention daily. A rehabilitation diary will be provided to record frequency and duration of treatment sessions and any other comments (see Appendix 2 for an example).

Weekly Zoom meetings will be agreed between the CRPS-participant, treatment partner, [name] and [name] (Cognitive Multisensory Rehabilitation Centre, Italy) in order to evaluate progress on the intervention and modify treatment plan if required (e.g. increasing the complexity of the tasks or adding new CMR tasks). [name] who will supervise the CMR treatment during the weekly zoom calls, providing further specialist CMR knowledge.

Session 2: Post-intervention clinical assessments

Following the four-week home-delivered intervention, CRPS patients and treatment partner will be invited to undergo the post-intervention clinical assessment session at the RUH in Bath. Post-intervention clinical assessments includes a repeat data collection of the self-reported measures completed at session 1 (see section Session 1).

Furthermore, CRPS-patients and treatment partner will be invited to attend an interview by [name] in order to gain insight in their experience of delivering/receiving CMR. The interview questions will be devised in order to gain insights on adherence, efficiency, acceptability, and safety of the intervention. This interview will include the discussion of:

- Content,
- Goals,
- Duration,
- Frequency and
- Modality of delivery of CMR

The anticipated total duration of session 1 is up to 1 hour.

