3.4 Analysis

Planned analyses specific to each study aim:

1. **To identify the suitability, feasibility of delivering CMR in people with CRPS.** In order to answer the overarching research question the total number of sessions, their duration and frequency will be described as well as the presence of any exacerbation of symptoms during the intervention will be recorded rehabilitation diary, which will be handed to the lead investigator during session 2.

Furthermore, descriptive comments regarding both delivering and receiving the intervention will be collected on the interview sessions, goals, duration, frequency and modality of delivery of CMR. The diary will be analysed in order to gain insight on the adherence, efficiency, acceptability, and safety of the intervention.

2. **To determine the feasibility of running an appropriately powered efficacy study on the effectiveness of CMR in CRPS.** In order to gain some

preliminary insights into the potential effectiveness of the intervention, we will inspect for each person the change in scores on each outcome measure, relative to clinically meaningful differences. Pre- and Post-intervention clinical assessments data will be described and summarized, and their distribution will be ascertained using IBM SPSS Statistics (SPSS Inc, Chicago USA).

4. Research procedure risks and benefits

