4.1 Anticipated risks

The potential risk for our patient participants is a temporary exacerbation of pain/discomfort, or nausea/dizziness related to the altered perception of their affected limb. These temporary changes should all settle within 24 hours after testing or the intervention. In the unlikely event that these effects persist for more than 48 hours, the participant will be advised to consult with their GP.

Procedures for recording incidents or adverse events

In the unlikely event that the participant experiences an adverse or unanticipated effect, they will be encouraged to contact the principal investigator ([name]) by phone or email who will provide advice. All symptoms and adverse events reported will be collected by the researchers and added to the participants' files. Both adverse effects related to the study (i.e. they resulted from the intervention administration or of any of the research procedures) and unexpected (i.e. not listed in the protocol as an expected occurrence) will be emailed to the research ethics committee (REC) within three days.

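### The example diary has no field for symptoms between sessions, for a flare's start and end, or for why a planned session was not held, although 3.4 makes it the record of exacerbations

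*Protocol*

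**What the plan says.** Four places in the protocol bear on this.

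- **3.3 Methods, Intervention phase.** The partner delivers the treatment at home over four weeks. Frequency is agreed with each pair and written in the treatment plan, and daily delivery is encouraged. On the diary: "A rehabilitation diary will be provided to record frequency and duration of treatment sessions and any other comments". Appendix 2 is cited there as an example.
- **3.4 Analysis, item 1.** "presence of any exacerbation of symptoms during the intervention will be recorded rehabilitation diary". The same item has the diary analysed for adherence, efficiency, acceptability and safety.
- **4.1 Anticipated risks.** The anticipated harm is a temporary rise in pain or discomfort, or nausea or dizziness. "These temporary changes should all settle within 24 hours after testing or the intervention". Effects that persist beyond 48 hours lead to advice to see the GP.
- **Appendix 2.** The page opens with "Please insert date and total duration of the session". Every other row belongs to a numbered task: whether it was completed (if not, "No, provide the reason"), time and repetitions, correctness of answers, and a yes/no adverse-effects item, "Any adverse effects (including symptom flare", with space to describe a yes.

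**The concern.** The form follows the session and the task, while the harm that 4.1 describes can run for a day or more after the session. A pair who finish a session without trouble, have a flare that evening and leave out the next day's session meet no prompt for either event.

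Aim b asks whether the intervention can be easily and safely delivered and received at home. A flare after a session, and a session not held because of one, are direct evidence on that aim. With five patients, one unrecorded flare changes the safety description noticeably, and a flare not written down at the time is hard to date later.

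**Working it through.** The protocol states no flare rate, power or capture rate, so there is no figure of its own to reproduce. The main check sets the form against the uses made of it.

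| What the text needs | Where stated | What Appendix 2 offers |
|---|---|---|
| Exacerbations during the intervention | 3.4 item 1 | Per-task yes (describe)/no item; nothing on symptoms since the last session |
| Whether effects settle within 24 h or last beyond 48 h | 4.1 | No prompt for start, end or duration |
| Session frequency and duration | 3.3, 3.4 item 1 | Date and duration of each session held |
| Insight into adherence | 3.4 item 1 | Reason for an uncompleted task; no line for a session not held |
| Any other comments | 3.3 | No general comments row |

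Only the third row is fully met. Under daily delivery, sessions are about 24 hours apart, so the settling window in 4.1 covers roughly the whole gap between two sessions. The form has no prompt for that gap.

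**What missed flares could do with five patients (illustration).** Inputs: n = 5 patients (Study sample); q = true share of patients with a flare (assumed); c = chance that an affected patient has a flare recorded (assumed), with patients independent. Then P(no patient with a recorded flare) = (1 − q·c)^5.

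| q | c = 1 | c = 0.75 | c = 0.50 | c = 0.25 |
|---|---|---|---|---|
| 0.2 | 32.8% | 44.4% | 59.0% | 77.4% |
| 0.4 | 7.8% | 16.8% | 32.8% | 59.0% |
| 0.6 | 1.0% | 5.0% | 16.8% | 44.4% |

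For q = 0.4 and c = 0.5: (1 − 0.2)^5 = 0.8^5 = 0.328.

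Even with full capture, 0 of 5 is weak evidence: the one-sided 95% upper bound is 1 − 0.05^(1/5) = 45.1%. Incomplete capture weakens it further.

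**What missed sessions do.** Suppose a pair agreed daily sessions: 4 × 7 = 28. Skipping 2, 4 or 7 leaves 26, 24 or 21 dated entries, which is 26/28 = 92.9%, 24/28 = 85.7% or 21/28 = 75.0% of plan. The shortfall is visible against the treatment plan. The form gives no way to say how much of it was due to flares.

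**The case against.** The case for leaving the form alone has real substance.

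- **The form captures more than it may seem to.** A flare that starts during a task can be described in free text, which can hold timing. A session broken off partway is covered by the per-task reason. Nothing forbids adding an evening flare to that day's page. All this stands: the gap concerns flares that start after the session, the absence of a timing prompt, and sessions never started.
- **A reader might infer that feasibility is flattered.** The documents do not support that. Entries are dated and the agreed frequency is on file, so skipped days lower the count against plan. Only the reason is lost.
- **A reader might infer that such flares go unrecorded by the study altogether.** That does not follow either. The contact route under 4.1 covers adverse or unanticipated effects, and Appendix 2 itself counts a flare as adverse, so expected flares qualify. The weekly calls include both members of the pair, and the final interview covers adherence and safety. But the contact route depends on the participant, the calls have a stated purpose of progress and plan changes with no adverse-event question, and the interview relies on recall over four weeks. They may catch some events without giving systematic or dated capture.
- **Appendix 2 is only an example.** True, and the issued diary may differ. It is nevertheless the model that 3.3 points to, and no other version is shown.
- **No analysis of time to settle is planned.** Also true. Formal 24 and 48 hour bands would be an extra analysis. The modest point is that the diary cannot reliably show whether the expectation in 4.1 was met.

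**Conclusion.** The point holds as a mismatch between the example form and the use made of it. Flares that start after a session are likely to be under-recorded in the diary, the 24 and 48 hour expectations cannot be reliably checked from it, and flare-related missed sessions cannot be separated from other missed sessions.

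The likely direction is that diary-based safety looks somewhat better than it was. That is a tendency, not a demonstrated result, and it does not extend to session counts. Its size cannot be derived from the documents. Over the assumed range, halving capture raises the chance of no recorded flare among five patients from 32.8% to 59.0% (q = 0.2), from 7.8% to 32.8% (q = 0.4) or from 1.0% to 16.8% (q = 0.6).

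This rests on the issued diary resembling Appendix 2. It is a worthwhile, inexpensive improvement and not a flaw that undermines the study.

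**What to change.** Revise Appendix 2 to one page per calendar day, whether or not a session took place, keeping the task rows and adding:

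1. *Any increase in symptoms since the last entry? When did it start, and when did it settle (or still present)?*
2. *Session held today? If not, reason (flare / partner unavailable / other).*
3. A general comments row, as 3.3 promises.

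In 3.4 item 1, add one sentence saying that flares will be described with their duration, and missed sessions by reason against the frequency agreed in the treatment plan. A standard symptom question at each weekly call would be a useful backstop.

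The cost is a revised page, one sentence, and about a minute more of diary completion per day. No treatment or clinical rule changes.

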Appendix 4: Recruitment packaged log

CRPS patient's name	Attended CRPS Initial Assessment (Y/N) If yes, please insert the date	Interested in participating? (Y/N)	Handed recruitment pack (Y?N) If yes, please insert the date	Attending CRPS rehabilitation program (Y/N)? If yes, please insert the date	Interested in participating? (Y/N)	Sent recruitment pack (Y/N) If yes, please insert the date
